3.4. Examination of Subject Subsets

No subgroup analyses are planned.

3.5. Multiple Comparisons

All endpoints will be tested at a 2-sided nominal significance level of 0.05, with no adjustment for multiple testing.

3.6. Missing Data

A missing data point for a given study visit may be due to any of the following reasons:

- A visit occurred in the window but data were not collected or were unusable
- A visit did not occur in the window
- A subject permanently discontinued from the study before reaching the window.

Missing values will not be imputed with the following exceptions:

- Missing day and month will be imputed for birth date in order to compute age as specified in Section 3.7
- If individual items are missing in the MLHFQ, the score will be computed as specified in Section 6.4.1.

The determination of treatment-emergence for AEs with incomplete dates is specified in Section 7.1.5.2.

3.7. Data Handling Conventions and Transformations

Baseline is defined as the last available record on or prior to the date of the first dose of study drug.

QT interval is affected by heart rate. Bazett's correction formula will be used to correct for heart rate.

Bazett's QT (QT_cB) correction formula:

$$QT_{cB} = \frac{QT}{\sqrt{RR}}$$

QT, RR, and other ECG parameters will be collected and adjudicated by the core ECG laboratory.

Pressure gradient for ECHO LV outflow tract will be computed using the modified Bernoulli equation:

$$\text{Pressure gradient (mmHg)} = 4 \times \text{Velocity (m/s)}^2$$

LA volume index will be computed as LA volume (mL) / body surface area (m²), where body surface area is computed using baseline height weight at the time of ECHO.

Body surface area (BSA) is computed as follows:

$$BSA = \sqrt{\frac{(\text{height (cm)} * \text{weight (kg)})}{3600}}$$

Age will be calculated as (Day 1 date – birth date) / 365.25, truncated to a whole number. If day for birth date is missing, set to the 1st day of the month. If both day and month are missing for birth date, set to January 1st. The randomization date will be used in lieu of Day 1 if the subject does not receive study drug. The informed consent date will be used if the subject is not enrolled.

Body mass index (BMI) is calculated as baseline weight (kg) / [height (m)]². BMI will be displayed to 1 decimal place in listings and summary statistics will be rounded to 1 decimal place, with the exception of standard deviation which will be rounded to 2 decimal places.

PK concentration values below the limit of quantitation (BLQ) will be treated as 0 at predose time points, and one-half the value of the lower limit of quantitation (LLOQ) at postbaseline time points for the determination of summary and order statistics. Individual values that are BLQ will be presented as "BLQ" in the concentration data listing. For the presentation of summary and order statistics, if at least one subject has a concentration value BLQ for the time point, then the minimum value will be displayed as "BLQ". If more than 25% of subjects have a concentration data value of BLQ for a given time point, then the minimum and first quartile [Q1] will be displayed as "BLQ." If more than 50% of the subjects have a concentration data value BLQ for

the time point, then the minimum, Q1, and median values will be displayed as “BLQ”. If more than 75% of the subjects have a concentration data value of BLQ for a given time point, then the minimum, Q1, median, and third quartile [Q3] values will be displayed as “BLQ”. If all subjects have concentration data values BLQ for the time point, then all order statistics (minimum, Q1, median, Q3, maximum) will be displayed as “BLQ”.

NT-proBNP and hsTnT results will be log-transformed.

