6.3. Randomization (Day 1)

The Randomization visit will occur within 14-28 days after the Screening visit on Day 1 (or within 14-60 days for subjects screening under Protocol Amendment 1). At the end of the Randomization visit, eligible subjects will be randomly assigned to receive GS-6615 or matching placebo.

The following will be performed and documented at the Randomization visit:

- Review inclusion and exclusion criteria to confirm continued eligibility
- Predose blood sample collection for plasma PK sample as described in Section 6.21 before the subject has taken the first dose of study drug
- **PPD**
- Urine pregnancy test for females of childbearing potential only
- Abbreviated physical examination including vital signs as described in Sections 6.18 and 6.19
- MLHFQ administration as described in Section 6.16
- Standard 12-lead resting ECG as described in Section 6.12
- For subjects with ICDs, perform ICD interrogation as described in Section 6.15
- Collect ZIO[®] XT Patch
- ZIO[®] XT Patch wear starts during the Randomization visit and continues for 14 days. Subjects will be provided with instructions for wear and removal of the patch. The ZIO[®] XT Patch will be collected at the Week 2 visit.
- Review of concomitant medications
- Review of adverse events
- After confirmation of eligibility, randomize subject via IXRS and dispense study drug. Provide subject with dosing instructions. Subject will take the Day 1 loading dose of study drug on site.
- Second blood sample collection for plasma PK sample as described in Section 6.21. The second PK sample should be collected 2-3 hours after the subject has taken the first dose of study drug. If 2-3 hours postdose collection is not possible, the second PK sample should be collected as late as possible before the subject leaves the clinic.
- Instruct the subject to hold the study drug dose on the day of the Week 2 visit so subject can take the study drug while on site.

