8.3. Data Handling Conventions

Baseline is defined as the Randomization visit value, if available, otherwise the Screening visit value serves as baseline.

Missing values for efficacy endpoints will be imputed by methods to be specified in the statistical analysis plan.

PK concentration values below the limit of quantitation (BLQ) will be treated as zero for the determination of summary statistics. Individual values which are BLQ will be presented as "BLQ" in the concentration data listing. For the presentation of summary and order statistics, if at least one subject has a concentration value BLQ for the time point, then the minimum value will be displayed as "BLQ." If more than 50% of the subjects have a concentration data value BLQ for the time point, then the minimum and median values will be displayed as "BLQ." If all subjects have concentration data values BLQ for the time point, then all order statistics (minimum, first quartile [Q1], median, third quartile [Q3], maximum) will be displayed as "BLQ."

NT-proBNP and hsTnT results will be log-transformed prior to analysis.

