8.6.2. Adverse Events

Adverse events will be coded using the Medical Dictionary for Regulatory Activities (MedDRA). System Organ Class (SOC), High-Level Group Term (HLGT), High-Level Term (HLT), Preferred Term (PT), and Lower-Level Term (LLT) will be attached to the clinical database.

Events will be summarized on the basis of the date of onset for the event. A treatment-emergent AE will be defined as any AE that begins on or after the date and time of first dose of study drug through 30 days after the last dose of study drug.

Summaries (number and percentage of subjects) of treatment-emergent AEs (by SOC, HLT and PT) will be provided by treatment group. Multiple AEs mapping to the same preferred term will be counted once per subject.

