3.8.2. Analysis Windows

Subject visits might not occur on protocol-specified days. Therefore, for the purpose of analysis, observations will be assigned to visits based on the windows presented in Table 3-1. Day 1 is the day of first dose of study drug.

Table 3-1. Visit Windows for Peak VO₂, MLHFQ, Treadmill Exercise Time, Biomarker Data, CPET 12-Lead ECG, and ICD Interrogation

Visit	Target Day	Visit Window in Day(s)
Baseline		≤ 1
Week 12	84	2–126
Week 24	168	> 126

Table 3-2. Visit Windows for ECHO

Visit	Target Day	Visit Window in Day(s)
Baseline		≤ 1
Week 2	14	2-49
Week 12	84	50–126
Week 24	168	> 126

Table 3-3. Visit Windows for Arrhythmia Burden

Visit	Target Day	Visit Window in Day(s)
Baseline		< 1
Days 1–14	1	1–21
Weeks 6–8	42	22–84
Weeks 18–20	126	> 84

The target and window are based on the start date of the 14-day ZIO[®] XT Patch period.

Table 3-4. Visit Windows for 12-Lead ECG, Vital Signs, and Clinical Laboratory Data

Visit	Target Day	Visit Window in Day(s)
Baseline		≤ 1
Week 2	14	2–28
Week 6	42	29–63
Week 12	84	64–105
Week 18	126	106–147
Week 24	168	148–210
Week 36	252	211–294
Week 48	336	295–378
Week 60	420	379–462
Week 72	504	463–546
Week 84	588	> 546 – last dose date + 30 days

All visits, including Unscheduled, Early Termination, and Follow-up visits, will be eligible for inclusion in table summaries based on the windows presented in Table 3-1, Table 3-2, and Table 3-3.

In the efficacy summary tables, Peak VO₂, treadmill exercise time, MLHFQ, ECHO, QTc interval at rest and at Peak from the exercise ECG, and biomarker results will be summarized based on values obtained at the visit using the windows in Table 3-1 or Table 3-2.

For the safety summaries, all visits other than the Follow-up visit, including Unscheduled and Early Termination visits, will be eligible for inclusion in table summaries based on the windows presented in Table 3-4.

In the safety summary tables for 12-lead ECG and vital signs, data obtained after the last dose date plus 30 days will be excluded from the summaries, but will be included in the listings.

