3.8.3. Selection of Data in the Event of Multiple Records in a Window

Depending on the statistical analysis method, single values may be required for each analysis window. A single value will be chosen based on the rules below.

If multiple nonmissing numeric observations exist in a window, a record will be chosen based on the following rules:

- For baseline, the last available record on or prior to the date of the first dose of study drug will be selected. If there are multiple records with the same time or no time recorded on the same day, average (arithmetic or geometric mean, as appropriate) will be used for the baseline value.
- For post baseline assessments:
 - The record closest to the target day for that visit will be selected.
 - If there are 2 records equidistant from the target, the later record will be selected.
 - If there is more than 1 record on the selected day, the average will be taken, unless otherwise specified.

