7.1.5. Treatment-Emergent Adverse Events

7.1.5.1. Definition of Treatment-Emergent

Treatment-emergent AEs are events that meet one of the following criteria:

- Any AEs with onset date of on or after the study drug start date and no later than 30 days after permanent discontinuation of study drug
- Any AEs leading to premature discontinuation of study drug.

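### The SAP's date-only Day 1 rules let an extra post-dose ECG or vital sign serve as baseline, and depart without declaration from the protocol's date-and-time rule for treatment-emergent AEs

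*SAP*

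**What the plan says.** **Baseline.** SAP 3.7 gives the general rule: "Baseline is defined as the last available record on or prior to the date of the first dose of study drug". SAP 3.8.3 repeats it for windows holding several records: "the last available record on or prior to the date of the first dose of study drug will be selected". It then adds: "If there are multiple records with the same time or no time recorded on the same day, average". SAP Table 3-4 (12-lead ECG, vital signs, laboratory data) sets baseline at Day 1 or earlier and opens the first post-baseline window on Day 2. SAP 3.8.2 admits unscheduled records: "For the safety summaries, all visits other than the Follow-up visit, including Unscheduled and Early Termination visits, will be eligible for inclusion". Protocol 8.3 words the rule differently: "Baseline is defined as the Randomization visit value, if available, otherwise the Screening visit value serves as baseline".

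**Day 1 procedures.** Protocol 6.3 lists one set of vital signs and one 12-lead ECG, then randomization and the on-site loading dose, then a PK draw: "The second PK sample should be collected 2-3 hours after the subject has taken the first dose of study drug". If that timing is not possible, the draw is made as late as possible before the subject leaves. Protocol 6.7 allows unscheduled assessments at the investigator's discretion, with AE evaluation as an example.

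**Treatment emergence.** Protocol 8.6.2 counts "any AE that begins on or after the date and time of first dose of study drug", through 30 days after the last dose. SAP 7.1.5.1 counts "Any AEs with onset date of on or after the study drug start date", with the same 30-day end.

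**The concern.** A baseline should precede treatment. On Day 1 the calendar date does not separate pre-dose from post-dose, because dosing happens during the visit and the subject is asked to remain for a later blood draw. If an ECG or blood pressure is repeated in that interval, the SAP makes the later reading the reference for every subsequent change. The reading then cannot appear as an early post-dose finding in the windowed summaries. At stake are the change-from-baseline summaries for vital signs (SAP 7.3) and ECG intervals (SAP 7.7.1), and the QTcB change categories in SAP 7.7.2, which count individual subjects.

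The AE rule has the mirror-image fault: an event that began on Day 1 before the dose counts as treatment-emergent. The protocol would not count it, and the SAP does not say that it has changed the rule.

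**Working it through.** The plan states no figure on this point. Its one design calculation concerns Peak VO2: 90 per arm, difference 3, SD 4, two-sided alpha 0.01. The noncentrality is 3 / (4 × √(2/90)) = 5.03, which gives power of 99.2% by the noncentral t with 178 df, against the stated figure of more than 95%. Nothing below affects it.

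**1. Does the rule exclude post-dose Day 1 records?** No. SAP 3.7 and 3.8.3 set the limit at the date of first dose. SAP 3.8.3 uses clock time to order same-day records and find ties, but not to drop those after dosing. So:
- both records timed: the later, post-dose record is selected;
- times equal or absent: the records are averaged;
- in either case the post-dose record falls in the baseline window and not in Week 2, which starts on Day 2.

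Returning to the protocol's wording would not help, because the Randomization visit value carries no pre-dose condition either.

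**2. Does the schedule produce such records?** Not if followed as written. Protocol 5.1 places first dosing at the end of the Randomization visit, and 6.3 lists the ECG and vital signs ahead of it. The systolic pressure and heart rate limits (inclusion criterion 7) and the atrial fibrillation exclusion (criterion 7) apply at that visit, so these measurements belong before dosing. The only measurement listed after dosing is the PK draw. However, the Day 1 order is implied and not mandated: a recommended order is given only for Weeks 12 and 24. Unscheduled assessments are also allowed. A post-dose record is possible but not planned.

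**3. Which variables can be affected?** The study procedures tables (Protocol Appendix 2, SAP Appendix 1) show:

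| Measure | Pre-treatment assessment | Exposed? |
|---|---|---|
| 12-lead ECG, vital signs | Screening and Day 1 | Yes, if an extra or out-of-order Day 1 record exists |
| Peak VO2, treadmill time | Screening | No |
| NT-proBNP, hsTnT | Screening | No |
| Laboratory tests | Screening | No |
| ZIO patch | Baseline window before Day 1 (SAP Table 3-3) | No |

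For the biomarkers this rests on the two tables. The narrative in SAP 1.2 mentions biomarker sampling on Day 1, which neither table shows.

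**4. Size and direction.** Let f be the share of an arm with a post-dose record taken as baseline, d the acute shift in that record, and e the true later effect. An affected subject's measured change is e − d, or e − d/2 if one pre-dose and one post-dose record are averaged. The arm mean moves by −f × d, or −f × d/2. The documents give neither f nor d for this population. If the schedule is followed, f = 0 and the shift is 0. As pure illustration, with f assumed at 0 to 10% and d at 10 msec, the mean moves by 0 to 1.0 msec, or 0 to 0.5 msec with averaging. The direction is not fixed: if e has the same sign as d and is larger, the change is understated; if it is smaller, the sign reverses.

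**5. AE rule.** Protocol 8.6.2 compares date and time; SAP 7.1.5.1 compares date. SAP 7.10 lists only dropped summaries, and the revision log in SAP 11 has no entry for 7.1.5. Before first dose, only SAEs and procedure-related AEs are recorded as AEs; other events go to medical history (Protocol 6.2.1, 7.3). The affected events are therefore those two kinds, on Day 1, before the dose. They arise before treatment and the rule is the same in both arms.

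**The case against.** The strongest reply is that this is a wording gap with little behind it. Followed as written, the schedule produces no post-dose Day 1 ECG or vital sign. A repeat on Day 1 could equally be a pre-dose recheck of an eligibility limit, which is a valid baseline. Safety comparisons are descriptive (SAP 7), and all planned listings are still produced (SAP 1), so a post-dose value remains visible by subject. For AEs, the protocol's source-record requirements (9.1.5) ask for start and end dates, not times. Where no onset time exists, a sensible fallback gives the same answer as the SAP rule. All of this stands and limits the point to minor. It does not make the baseline rule right when such a record exists, and it does not explain the undeclared departure from protocol 8.6.2.

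Three stronger readings are tempting, and the documents do not support them.

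- *That post-dose baselines are routine.* The schedule points the other way, and no document gives a frequency of repeat Day 1 recordings or says why they would be made.
- *That each affected baseline is shifted by about 30 msec.* Under assumed dose proportionality, a 30 mg dose gives a Cmax of 655 × 30/60 = about 328 ng/mL, near the 362 ng/mL that protocol 1.3.1 links to average QTc shortening of 30 msec. But that is a Day 7 daytime average in LQT3 subjects. The protocol argues that late sodium current enhancement is similar in HCM, but reports no QTc measurement there. Protocol 1.2.3 reports no clinically significant ECG findings or trends in healthy elderly subjects given a loading dose and then 6 mg daily. Neither population settles the size of an early effect in HCM.
- *That the bias runs towards no effect.* On the same assumption, the post-load level of about 328 ng/mL exceeds the 234 ng/mL anticipated on 3 mg. If QTc shortens with concentration, a post-load baseline would make later values on 3 mg look longer.

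**Conclusion.** The point holds as a minor defect of definition. The SAP's baseline rule accepts a Day 1 ECG or vital sign taken after the loading dose, by replacement or by averaging, and keeps it out of the post-baseline windows. It matters only for subjects with an unscheduled or out-of-order recording. How many there are is unknown and may be none, and neither the size nor the direction of any bias can be stated from the documents. The primary endpoint and the other measures marked as not exposed are untouched, provided the study procedures tables were followed.

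The AE definition contradicts the protocol and the change is undeclared. Its effect is a possible slight over-count of treatment-emergent events from pre-dose Day 1 SAEs and procedure-related AEs. No difference between arms is expected from it.

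**What to change.** Before unblinding:

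1. In SAP 3.7 and 3.8.3, define baseline as the last non-missing record before the date and time of first dose. For untimed Day 1 records, use the scheduled Randomization-visit record and do not average unscheduled Day 1 records into it.
2. In SAP 7.1.5.1, use date and time of first dose where the AE onset time is recorded, and keep untimed Day 1 events as treatment-emergent. Alternatively, keep the date-only rule and list it in SAP 7.10 as a change from protocol 8.6.2.

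The cost is a few words and a small programming change. SAP 2 has the blind broken only after the data are finalized, so there is room to do it. The baseline change assumes that the Day 1 dose time was captured, which the timed PK draw implies but the documents do not state; the untimed-record rule covers gaps in ECG and vital sign times. The AE change alters counts only where onset times exist, so if they were not collected, declaring the date-only rule is the practical choice.

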HLGH	high-level group term
HLT	high-level term
hr	hour
HR	heart rate
hsTnT	high-sensitivity Troponin T
ICD	implantable cardioverter-defibrillator
ICH	International Conference on Harmonisation
IEC	independent ethics committee
IMP	investigational medicinal product
I _{Na}	sodium current
IND	Investigational New Drug

IRB	institutional review board
IUD	intrauterine device
IXRS	Interactive Voice/Web Response System
kg	kilogram(s)
LA	left atrial
late I_{Na}	late sodium current
LLT	lower-level term
LQTS	long QT syndrome
LQT3	long QT3
LV	left ventricular
LVOT	left ventricular outflow tract
MAD	multiple ascending dose
MDRD	modification of diet in renal disease
MedDRA	Medical Dictionary for Regulatory Activities
mg	milligram
mL	milliliter
MLHFQ	Minnesota Living with Heart Failure Questionnaire
mm	millimeter
mmHG	millimeter of mercury
MMRM	mixed models repeated measurement
msec	millisecond
Na^+	sodium
ng	nanogram
NOAEL	no observed adverse effect level
nsVT	non-sustained ventricular tachycardia
NT-proBNP	N-terminal-pro-brain natriuretic peptide
NYHA	New York Heart Association
O_2	oxygen
OLE	open-label extension
PD	pharmacodynamic(s)
Peak VO_2	peak oxygen consumption
PE	physical examination
PG	pharmacogenomic(s)
PK	pharmacokinetic(s)
PR interval	electrocardiographic interval occurring between the onset of the P wave and the QRS complex representing time for atrial and ventricular depolarization, respectively
PT	preferred term
PVC	premature ventricular complex
Q1	first quartile

Q3	third quartile
QRS	electrocardiographic deflection between the beginning of the Q wave and termination of the S wave representing time for ventricular depolarization.
QT	electrocardiographic interval between the beginning of the Q wave and termination of the T wave representing the time for both ventricular depolarization and repolarization to occur
QTc	QT interval corrected for heart rate
QTcF	QT interval corrected for heart rate using the Fridericia formula
RER	respiratory exchange ratio, the ratio carbon dioxide production to oxygen consumption (VCO_2/VO_2)
RR	respiratory rate
RR interval	electrocardiographic interval representing the time measurement between the R wave of one heartbeat and the R wave of the preceding heartbeat
RV	right ventricular
SAD	single ascending dose
SADR	serious adverse drug reaction
SAE	serious adverse event
SBP	systolic blood pressure
SCD	sudden cardiac death
SD	standard deviation
SOC	System Organ Class
SOP	standard operating procedure

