8.1.5. Safety Endpoints

The safety endpoints include:

- Mortality and Appropriate ICD interventions (Shock or Anti-Tachycardia Pacing)
- AEs
- Vital Signs
- Clinical Laboratory Tests
- ECG data (PR, RR, QRS, QT and QTc interval).

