7.7. Electrocardiogram Results

The following analyses of 12-lead ECG results are intended to identify gross changes in QT interval and other ECG characteristics. If potential abnormalities of interest are identified, further analyses may be conducted. Summaries of continuous ECG results (RR, PR, QRS, QT, and QTcB) will be provided for the safety analysis set using descriptive statistics (sample size, mean, standard deviation, median, Q1, Q3, minimum, and maximum) by treatment group for each post-baseline analysis visit.

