7.7.1. Corrected QT Intervals

The QT interval (measured in msec) will be corrected for heart rate as indicated in Section 3.7 using Bazett's formula.

QTcB, and uncorrected QT values at each visit and change from baseline at each visit will be summarized for the safety analysis set by treatment group using descriptive statistics (sample size, mean, standard deviation, median, Q1, Q3, minimum, and maximum).

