7.7.2. Prolonged QT Intervals and QT, PR and QRS Intervals

The number (%) of subjects with core laboratory ECG values, and change from baseline in the ranges shown in the table below will be summarized by treatment group at each visit.

PR Interval (msec)	QRS Interval (msec)	QT _c B (msec)	QT _c B Change from Baseline (msec)
< 200	< 120	> 450	< -60
≥ 200	≥ 120	≥ 480	≥ -30
≥ 220		≥ 500	≥ 0
			≥ 30
			≥ 60

Categorical ECG abnormalities (borderline and prolonged QTcB, PR ≥ 200, PR ≥ 220, QRS ≥ 120, QTcB > 450, QTcB ≥ 480, QTcB ≥ 500, QTcB change from baseline ≥ 30, QTcB change from baseline ≥ 60) will be flagged in the corresponding listing.

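### The SAP corrects QT by Bazett alone, without explaining why the protocol glossary lists Fridericia; reporting QTcF beside QTcB would stop QTc counts resting on one heart-rate-sensitive formula

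*SAP*

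**What the plan says.** SAP 3.7 gives a single rule: Bazett's "correction formula will be used to correct for heart rate", with QT divided by the square root of RR. No unit is given for RR. SAP 7.7.1 refers back to it: "The QT interval (measured in msec) will be corrected for heart rate as indicated in Section 3.7".

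QTcB is then the only corrected QT in the visible analysis text:

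- SAP 5.1 lists it as a baseline characteristic.
- SAP 7.7 and 7.7.1 summarise it by visit. The latter says "QTcB, and uncorrected QT values at each visit and change from baseline at each visit will be summarized".
- SAP 7.7.2 applies the outlier limits to it, "QTcB > 450, QTcB ≥ 480, QTcB ≥ 500", with change-from-baseline categories that include ≥ 30 and ≥ 60 msec.

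SAP 3.8.2 also places "QTc interval at rest and at Peak from the exercise ECG" among the summarised results. The general rule in SAP 3.7 would cover that too.

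The protocol's safety endpoint (8.1.5) refers to QTc without a formula. The only correction the protocol names is in its glossary, where QTcF is the "QT interval corrected for heart rate using the Fridericia formula". The SAP does not mention Fridericia. Its lists of changes from protocol (6.6 and 7.10) and its revision log (11) say nothing about the QT formula.

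**The concern.** The two formulas agree only at 60 bpm. Elsewhere they differ by an amount that depends on heart rate, so a change in heart rate alone can register as a change in one corrected QT and not the other. QTc is a named safety endpoint, and QTc shortening in LQT3 is part of the dose rationale in Protocol 1.3.1, so readers will look closely at these tables.

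At stake are the within-arm changes in QTcB, the counts above 450 msec and the counts with a rise of at least 30 msec. With one formula, a reader cannot tell how far these depend on the correction chosen.

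**Working it through.** The documents give no figure for the size of this effect, so there is none to reproduce. The QTcF levels, heart rates and exponents below are assumptions for illustration.

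**1. Ratio of the formulas.** With RR = 60/HR in seconds, QTcB = QT/RR^(1/2) and QTcF = QT/RR^(1/3). Hence QTcB/QTcF = RR^(-1/6) = (HR/60)^(1/6).

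**2. Resting rates.** Hold QTcF constant, so that Fridericia is taken as exactly right. The heart-rate limit at entry (inclusion criterion 7) is 100 bpm. Steps are from unrounded values.

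| HR (bpm) | Ratio | QTcB if QTcF = 420 | Step per 10 bpm | QTcB if QTcF = 440 |
|---|---|---|---|---|
| 50 | 0.9701 | 407.4 | – | 426.8 |
| 60 | 1.0000 | 420.0 | 12.6 | 440.0 |
| 70 | 1.0260 | 430.9 | 10.9 | 451.5 |
| 80 | 1.0491 | 440.6 | 9.7 | 461.6 |
| 90 | 1.0699 | 449.4 | 8.7 | 470.8 |
| 100 | 1.0889 | 457.3 | 8.0 | 479.1 |

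**3. Crossing the 450 msec limit.** The crossing rate is 60 × (450/QTcF)^6. For QTcF 420 this is about 91 bpm, and for QTcF 440 about 69 bpm. Both lie within the rates allowed at entry.

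**4. Dependence on the true QT-RR relation.** Suppose QT = 430 × RR^a. A formula with exponent e then gives QTc = 430 × (60/HR)^(a − e). For a fall from 65 to 60 bpm, the spurious change in msec is:

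| True exponent a | Bazett | Fridericia |
|---|---|---|
| 0.25 | −8.7 | −2.9 |
| 1/3 | −5.8 | 0.0 |
| 0.40 | −3.5 | +2.3 |
| 0.45 | −1.7 | +4.0 |
| 0.50 | 0.0 | +5.7 |

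The two do about equally well midway between the exponents, at (1/3 + 1/2)/2 ≈ 0.417. Below that Fridericia is closer; above it Bazett is.

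**5. Is a heart-rate shift plausible?** Compare the conditions of the resting ECGs.

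- *Baseline.* SAP 3.7 takes the last record up to first dose. That is normally the Randomization ECG (Protocol 6.3), a visit with no exercise test and no instruction to withhold medication other than study drug.
- *Weeks 12 and 24.* Protocol 6.4.5 and 6.4.9 recommend the ECG directly before the exercise test, and Protocol 6.11.2.1 asks subjects to withhold all medication that morning. Beta-blockers and calcium channel blockers are allowed (Protocol 5.4).

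A higher resting rate at those two visits, in both arms, is therefore plausible. The documents give no size for it.

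**6. Peak exercise.** At 120 to 150 bpm QTcB is 12 to 17% above QTcF. Peak is compared with baseline peak, however, so most of this cancels in the change. With QTcF at 430 msec, a fall in peak rate from 130 to 120 bpm moves QTcB by −6.5 msec, and from 140 to 130 bpm by −6.1 msec. The withholding instruction also applies to the Screening exercise test, so step 5 gives no reason to expect a shift in the exercise ECG.

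**The case against.** The strongest reply has four parts.

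*No protocol departure is shown.* A reader might infer that the SAP replaced a correction the protocol had specified. The documents do not support that. Fridericia is only an abbreviation; the readable operative text says QTc; and the exploratory endpoint and analysis sections of both documents are blacked out. What stands is an unexplained inconsistency.

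*The artefact is conditional.* A reader might also infer that heart-rate differences will appear as QTc change. That needs an actual heart-rate shift and an exponent below 0.5. The documents give no heart-rate effect of the drug and no exponent, and they recommend stable doses of background medication. The table in step 2 assumes Fridericia is right; step 4 shows that near 0.5 Fridericia is the worse formula. This stands in full.

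*Existing safeguards.* RR and uncorrected QT are summarised by arm and visit, ECG results are listed, SAP 7.7 allows further analyses, and a concurrent placebo arm should share a common shift. This stands in part. Mean RR and QT do not reclassify a subject counted above 450 msec, the further analyses are undefined, and exercise-test heart rate is listed but not summarised (SAP 7.4 and 7.10).

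*Low consequence.* SAP 7 plans no formal safety comparisons, SAP 6.6 removes inference from exploratory endpoints, and the study was terminated and is to have a synoptic report. This stands and limits the weight of the point.

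**Conclusion.** The point holds as a cheap improvement to descriptive output. The SAP relies on one heart-rate-sensitive correction, does not explain it, and does not reconcile it with the protocol glossary.

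If QTcF is constant at 420 msec, QTcB moves by about 8 to 13 msec per 10 bpm between 50 and 100 bpm, and it passes 450 msec at about 91 bpm (about 69 bpm if QTcF is 440). This rests on heart rate shifting from baseline and on a true exponent nearer 1/3 than 1/2.

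A shift common to both arms would largely cancel in the between-arm mean difference, but it would remain in within-arm changes and threshold counts. It would be wrong to conclude that the treatment comparison is biased, or that values at peak exercise inflate the 450, 480 and 500 msec counts: those limits belong to the resting 12-lead section. The primary and secondary endpoints are untouched. The documents do not establish that Bazett should be replaced.

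**What to change.** - In SAP 3.7, keep QTcB and also derive QTcF = QT/RR^(1/3), stating that RR is in seconds for both formulas.
- Report QTcF beside QTcB in SAP 5.1, 7.7, 7.7.1 and 7.7.2, and for QTc at rest and at peak from the exercise ECG.
- Apply the same level and change thresholds to both.
- State the choice of formula, and its relation to the protocol glossary, in SAP 6.6 and 7.10.

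The core ECG laboratory already supplies QT and RR, so no new data are needed. The cost is one derived variable and one more column per ECG table.
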